1 RESEARCH PURPOSE

Primary purpose: To evaluate the safety and tolerability of different doses of REGEND001 autologous therapy product for the treatment of idiopathic pulmonary fibrosis (IPF).

Secondary purpose: To assess the efficacy of different doses of REGEND001 autologous therapy product for the treatment of IPF and recommend appropriate cell therapy doses for subsequent clinical studies.

1.1 STUDY DESIGN

Multicenter, open-label, dose-escalation, exploratory clinical research.

1.2 OVERALL DESIGN

This study is an open-label clinical research on the safety, tolerance, and primary efficacy of REGEND001 autologous therapy product treating idiopathic pulmonary fibrosis, with a follow-up period of 24 weeks.

1.3 DOSE-ESCALATION GROUPS

The standard dose of REGEND001 autologous therapy product is 1×10^6 cells /kg bodyweight /person.

Each dose group will enroll around 3-6 patients. Before starting the next dose group, safety evaluation must be done for 3 patients of the current dose group at 4 weeks post-transplantation. If 1 patient from a certain dose group undergo adverse events that would terminate the study within the evaluation window (28 days after receiving REGEND001 autologous therapy product), 3 more patients should be enrolled for this dose group; the next dose group cannot start unless none of the new enrolled 3 patients undergo adverse events that would terminate the study.

The first group with 3-6 patients, receiving a single administration at 0.6 times standard dose;

The second group with 3-6 patients, receiving a single administration at 1 times standard dose (the median safe dose in the previous clinical trial);

The third group with 3-6 patients, receiving a single administration at 2 times standard dose;

The fourth group with 6 patients, receiving a single administration at 3.3 times standard dose;

The following doses will be arranged according to the safety measures of these 4 dose groups.

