Follow-up stage: The patients will stop receiving REGEND001 during the follow-up stage, and continue with usual treatment which can be adjusted according to the doctor's orders.

Each patient will be followed up for 24 weeks after the administration, with a total of 5 visits. The follow-up time points

including V5 (24 hours \pm 4 hours after transplantation), V6 (1 week \pm 2 days after transplantation), V7 (4 weeks \pm 3 days after transplantation), V8 (12 weeks \pm 5 days after transplantation), and V9 (24 weeks \pm 7 days after transplantation). During the study, check and record the vital signs, laboratory examinations, 12-lead electrocardiogram, chest HRCT, pulmonary functions, 6-minute walking distance, questionnaires, concomitant medications, adverse events, etc.

If the patients undergo adverse events/severe adverse events, the situation should be documented in detail and followed up until the outcome is clear.

Safety follow-up stage after research: After the end of the follow-up stage in this study, the patient will enter the post-study safety follow-up until the patient's death or lost. The patient will be followed up once each at 1, 2, 3, 5, 8, and 10 years after treatment, and then once every five years.

Study Flowchart-----Each Dose Group

	Screening Stage	Cell Collection Stage	Baseline Stage ¹⁷	Cell Transplantation Stage	Follow-up Stage					
Content	14 days	1 day	0-5 days before transplantation	1 day	24 hours ± 4 hours after transplantation	1 week ± 2 days after transplantation	4 week ± 3 days after transplantation	12 week ± 5 days after transplantation	24 week ± 7 days after transplantation	Withdraw in advance ¹⁸
Stage Code	V1	V2	V3	V4	V5	V6	V7	V8	V9	
Sign Informed Consent	X									
Check Inclusion/Exclusion Criteria	X		X							
Demographic Characteristics ¹	X									
Medical History and Diagnosis ²	X									
Symptoms and Physical Examination ³	X	X	X	X	X	X	X	X	X	X
Vital Signs ⁴	X	X	X	X	X	X	X	X	X	X
Blood Routine, Urine Routine ⁵	X		X			X	X	X	X	X
Blood Chorionic Gonadotropin Blood Test ⁶	X		X						X	X
Blood Biochemistry Test ⁷	X		X			X	X	X	X	X
Arterial Blood Gas Test ⁸			X					X	X	X

Adverse Events		X	X	X	X	X	X	X	X	X
Severe Adverse Events		X	X	X	X	X	X	X	X	X

Note:

1. Including date of birth, gender, and ethnic.
2. Medical history: history of the present illness, past medical history, history of food and drug allergies, smoking history, drinking history, drug history, history of substance abuse.

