1.6 CRITERIA FOR DOSE ESCALATION TERMINATION

(1) Adverse events that occurred throughout the study period were assessed and graded according to CTCAE V5.0. Dose escalation should be terminated with one or more adverse events that were the same or similar and believed to be related (possibly, probably or definitely related) to the REGEND001 autologous therapy product reported on two or more patients of the same dose group after autologous transplantation:

1) hematological toxicity related to cell therapy

a) grade 4 neutropenia (ANC) for 3 days or more; or grade 3 and higher neutropenia with fever ($ANC < 1000/mm^3$ with a single measure of oral temperature $> 38.3^\circ C$ or $\geq 38.0^\circ C$ for one hour);

b) grade 3 thrombocytopenia ($25 \times 10^9/L \leq$ platelet counting $< 50 \times 10^9/L$) with overt clinical bleeding symptoms, or grade 4 thrombocytopenia (with or without overt clinical bleeding symptoms);

c) other grade 4 hematological toxicity.

2) non-hematological toxicity related to cell therapy

grade 3 and higher non-hematological toxicity, except:

a) under medical intervention, grade 3 non-hematological toxicity lasting ≤ 72 hours (non-laboratory examination, such as nausea, vomiting, or diarrhea, etc.);

b) under medical intervention, grade 3 or 4 non-hematological toxicity of abnormal in laboratory examination lasting ≤ 7 days (laboratory examination, such as arrhythmia, cardiac insufficiency, and nervous system abnormalities);

c) other toxicity that is higher than baseline level and related to cell therapy, classified as clinically meaningful severe and/or unacceptable toxicity by investigator and sponsor.

(2) Acute IPF exacerbation and severe adverse events that are related (possibly, probably or definitely related) to REGEND001 cell therapy;

(3) Adverse events that making investigator and sponsor believe the dose should not be escalated anymore, regardless of the event grade or reason;

(4) If none toxicity that would terminate dose escalation happened under the highest 3.3 times standard dose, investigator and sponsor will discuss together regarding

whether dose escalation should continue; if discontinued, the study will stop.

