9 CRITERIA FOR STUDY TERMINATION/DISCONTINUATION

The trial may be prematurely halted or terminated if there are sufficient reasons, including but not limited to the following:

(1) Occurrence of toxic reactions that meet the criteria for terminating dose escalation during the trial.

(2) Insufficient funding, patent disputes, or changes in national pharmaceutical development policies by the sponsor.

(3) Regulatory authorities or ethics committees request the suspension or termination of an approved trial.

In addition, the sponsor reserves the right to suspend or terminate the trial at any time.

Once the issues causing the trial suspension or termination, such as drug safety or protocol non-compliance, are resolved and approved by the sponsor, ethics committees, and regulatory authorities, the trial may resume.

After deciding to suspend or terminate the trial, any party involved (including but not limited to the sponsor, investigators, ethics committees, and regulatory authorities) should immediately issue a written notification to the other parties, providing the relevant reasons.

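### Section 1.3 does not define the single-patient event that expands a dose group, and the protocol does not say whether one related exacerbation or severe event expands the group or stops escalation (1.6(2))

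*Protocol*

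**What the plan says.** Protocol 1.3 (dose-escalation groups) gives the expansion rule. Three patients are treated and assessed at four weeks. The trigger reads "If 1 patient from a certain dose group undergo adverse events that would terminate the study within the evaluation window", and the window is 28 days from administration. The action is to enrol three more at the same dose, after which "the next dose group cannot start unless none of the new enrolled 3 patients undergo adverse events that would terminate the study". Section 1.3 neither defines the event nor refers to another section.

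Protocol 1.6 (criteria for dose escalation termination) lists the stopping criteria:

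- 1.6(1): "Dose escalation should be terminated with one or more adverse events that were the same or similar and believed to be related" to the product, and "reported on two or more patients of the same dose group after autologous transplantation". A list of haematological and non-haematological toxicities follows.
- 1.6(2): "Acute IPF exacerbation and severe adverse events that are related (possibly, probably or definitely related) to REGEND001 cell therapy". No number of patients is given.
- 1.6(3): "Adverse events that making investigator and sponsor believe the dose should not be escalated anymore, regardless of the event grade or reason".

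Protocol section 9, item (1), gives as a reason for halting the trial: "Occurrence of toxic reactions that meet the criteria for terminating dose escalation during the trial". This is the stated link from study termination for toxicity back to 1.6.

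**The concern.** Section 1.3 acts on one patient. The criteria it appears to lean on either need two patients or, once met, already end escalation. If 1.3 is taken to mean that a 1.6 criterion has been met, one patient cannot trigger it through 1.6(1). One patient can trigger it through 1.6(2), but that criterion says escalation is over, while 1.3 describes a route by which the next dose might still open. No section says which prevails.

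Safety and tolerability by dose is the primary purpose (section 1), and this rule decides whether the next patients receive a higher dose. The case at issue is not trivial: section 15.2.5 describes acute exacerbation of IPF as severe with high mortality. In a multicentre, open-label escalation, two investigators could each follow the text after one related exacerbation and act differently.

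**Working it through.** **The plan's own figure.** Groups 1 to 3 have 3 to 6 patients and group 4 has 6 (section 1.3). Minimum 3 + 3 + 3 + 6 = 15; maximum 4 × 6 = 24. This reproduces the 15 to 24 in sections 1.7 and 17.1, so expansion from 3 to 6 is built into the design and is meant to operate.

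**What one patient can trigger.**

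| Criterion | Can one patient meet it? | Stated consequence |
|---|---|---|
| 1.6(1) | No: two or more patients, same or similar event | Escalation ends |
| 1.6(2) | Yes: no patient count | Escalation ends |
| 1.6(3) | Yes, if investigator and sponsor so judge | Escalation ends |
| 1.3 | Yes: one patient, event undefined | Add 3; next dose barred unless those 3 are clean |

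Every 1.6 criterion that one patient can meet ends escalation. The expansion in 1.3 therefore has a purpose of its own only if its trigger means a type of event and not a criterion already met. The text does not say this.

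**The word severe in 1.6(2).** Section 11.3 uses that word for CTCAE grade 3; section 12.1 defines serious adverse events separately. In the grading sense, one related grade 3 event would stop escalation, which would bypass the two-patient threshold of 1.6(1) and its exceptions for short-lived grade 3 toxicity. Section 1.4 pairs the terms ("If the patients undergo adverse events/severe adverse events, the situation should be documented in detail"), as do the flowchart rows, which suggests that serious was meant.

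**Illustration of size.** The protocol states no event rate. Assume each patient independently has probability p of a related 1.6(2) event within 28 days, with p = 0.10, 0.20 or 0.33, in a group that starts with three.

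- One event stops: P(escalate) = (1−p)³.
- 1.3 governs a single event (0 of 3, or 1 of 3 then 0 of 3 added; two or more of the first three do not escalate): P(escalate) = (1−p)³ + 3p(1−p)⁵.
- Exactly one of the first three: 3p(1−p)².
- Opposite final decisions (one of the first three, none of the added three): 3p(1−p)⁵.

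| p | One event stops | 1.3 governs | Exactly one of first 3 | Opposite decisions |
|---|---|---|---|---|
| 0.10 | 0.729 | 0.729 + 0.177 = 0.906 | 0.243 | 0.177 |
| 0.20 | 0.512 | 0.512 + 0.197 = 0.709 | 0.384 | 0.197 |
| 0.33 | 0.301 | 0.301 + 0.134 = 0.434 (unrounded terms) | 0.444 | 0.134 |

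The last column equals the difference between the two rules.

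**The case against.** The strongest reply is that the text can be obeyed as it stands. The 1.3 clause that bars the next group sets a necessary condition for escalating; it does not grant permission. After one related exacerbation a site could enrol three more at the same dose and still not escalate, satisfying both 1.3 and 1.6(2). In addition, 1.3 supplies its own patient count, so its event phrase most naturally refers to a type of event. Read with 1.6(1), that gives a familiar pattern: one patient expands, two with similar events stop. The group sizes fit it. Section 1.6(3) also allows a discretionary stop.

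Most of this stands, and it limits the point. A reader might infer that the expansion step is inoperable, or that the protocol positively authorises escalation after a related exacerbation. The documents support neither. Nor is 9(1) the only possible meaning of study termination: the list in section 9 is expressly not exhaustive and the sponsor may stop at any time, while section 2.4.1(2) lets an investigator withdraw a patient for an adverse event. Those routes are loose, however, and they add candidate meanings without settling one.

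What the reply does not remove is that the sensible reading is unstated. The condition about the added three is of little use unless escalation can follow when it is met, and nothing says that 1.6(2) overrides it. Discretion under 1.6(3) sets no default.

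The assumed rates can also be challenged. Section 15.2.3 reports no study-related complications in earlier clinical research, and 1.3 describes the standard dose as the median safe dose of a previous trial. Nothing in the protocol supports the upper end of the range at the lower doses.

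**Conclusion.** The point holds as an undefined trigger and an unstated order of precedence in a dosing rule that the protocol itself sets. One related acute exacerbation or severe adverse event can be handled as expand and possibly escalate, or as a stop. It should be fixed, but it does not make the design unworkable, because a conservative and coherent reading is available.

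The conclusion rests on the wording of 1.3, 1.6 and 9(1) and on no event rate. The 18%, 20% and 13% of dose groups with opposite decisions depend on assumed rates of 10%, 20% and 33%, on independence between patients, and on 1.3 being read as allowing escalation after a clean expansion. A reader might take them as expected frequencies in this trial; the protocol gives no basis for that, and they carry no weight in how serious the point is.

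**What to change.** - **1.3:** define the trigger as one patient with a related event of a type listed in 1.6(1) within 28 days of administration; this expands the group by three.
- **1.3 and 1.6(1):** state that two or more patients in the group with such events stop escalation, whether or not the events are similar. If the similarity condition stayed, two patients among the first three with different qualifying events would fall under neither rule: 1.3 speaks of one patient and 1.6(1) requires similarity.
- **1.6(2):** state that one related acute IPF exacerbation or serious adverse event, as defined in section 12, stops escalation and overrides 1.3. This replaces the word severe and keeps the stop that 1.6 already states as the default.
- **9(1):** cite the same rule.

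The cost is a wording amendment to 1.3, 1.6 and 9(1), and somewhat more frequent expansion or stopping. The planned range of 15 to 24 patients need not change, because it already allows each of the first three groups to grow to six.

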11.2 COLLECTION AND RECORDING OF ADVERSE EVENTS

Monitoring of Adverse Events (AE) will be conducted throughout the entire study, and it is the responsibility of the investigators to record all AEs observed during the study period. Any adverse medical events occurring from the initiation of autologous cell collection until the end of follow-up, regardless of severity or causal relationship with the investigational drug, must be documented in the medical records. Detailed documentation of the following information is required for all AEs:

- **AE Description:** Describe the AE using medical terminology rather than the language reported by the subjects. If applicable, include symptoms, signs, abnormal laboratory findings, and diagnosis. If the same AE occurs more than once in a subject and the subject has recovered between the two events, each occurrence should be recorded separately.

- **AE Onset Date:** The date when the subject first experienced the AE or when symptoms related to the AE appeared. If the AE is a clinically significant abnormal laboratory finding or test result, the date of sampling should be recorded.
- **AE Outcome Date:** The date of resolution of the AE or when symptoms related to the AE improved. If the AE is still ongoing, the outcome date does not need to be filled.
- **Severity of AE.**
- **Causal Relationship between AE and the investigational drug.**
- **Actions Taken:** (1) Actions taken with regard to the investigational drug: continued use, discontinued use, treatment completed, not applicable; (2) Actions taken regarding the AE: none, medication treatment, non-drug treatment.
- **Outcome of AE:** Disappeared, recovery with sequelae, improvement, stable, aggravated, death, subject refusal for follow-up or lost to follow-up, unknow.

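### The 28-day expansion window in section 1.3 can close up to three days before the 4-week visit whose laboratory results feed the escalation gate

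*Protocol*

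**What the plan says.** Protocol 1.3 sets the gate: before the next dose group starts, "safety evaluation must be done for 3 patients of the current dose group at 4 weeks post-transplantation". It then sets the expansion rule: if one patient in the group has an event of the stopping type "within the evaluation window (28 days after receiving REGEND001 autologous therapy product), 3 more patients should be enrolled for this dose group". The next group opens only if none of the three added patients has such an event.

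The flowchart in 1.4 places V7 at "4 week ± 3 days after transplantation". Routine blood, urine and biochemistry tests are scheduled at V6 (1 week ± 2 days), V7 and V8 (12 weeks ± 5 days).

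On dating, 11.2 says: "If the AE is a clinically significant abnormal laboratory finding or test result, the date of sampling should be recorded". Other events are dated from first experience or first symptoms.

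The stopping criteria are in 1.6:

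- 1.6(1) lists related toxicities and stops escalation when the same or similar one is "reported on two or more patients of the same dose group after autologous transplantation". Its exemptions include "under medical intervention, grade 3 or 4 non-hematological toxicity of abnormal in laboratory examination lasting ≤ 7 days".
- 1.6(2) covers related acute exacerbations and severe adverse events.
- 1.6(3) covers "Adverse events that making investigator and sponsor believe the dose should not be escalated anymore, regardless of the event grade or reason".

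**The concern.** The gate and the expansion rule are meant to work together: three patients are assessed at 4 weeks, and one qualifying event adds three more at the same dose. But the gate is tied to a visit with a tolerance of three days either way, while the expansion rule is tied to a fixed 28 days with none. The visit that supplies the gate's scheduled laboratory data can therefore take place after the window in which a finding has automatic effect.

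At stake is whether a pre-specified safety rule depends on the appointment day. Without expansion, and without a discretionary stop, the next patients go to a dose 1.65 to 2 times higher instead of three more being treated at the current dose.

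**Working it through.** **Inputs.** Expansion window: 28 days after administration (1.3). V6: day 7 ± 2. V7: day 28 ± 3. V8: day 84 ± 5 (all 1.4). Laboratory onset is the sampling date (11.2). Group sizes are 3-6, 3-6, 3-6 and 6 (1.3). Doses are 0.6, 1, 2 and 3.3 times standard (1.3).

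**The plan's own figure.** Minimum 3 + 3 + 3 + 6 = 15; maximum 6 × 4 = 24. This reproduces the 15 to 24 patients in 1.7 and 17.1.

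**Visit days against the window.**

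- V7 is permitted from 28 − 3 = 25 to 28 + 3 = 31, which is 7 days.
- Days after the window closes are 29, 30 and 31, so 3 of 7.
- V6 falls on days 5 to 9. With V7 on days 29 to 31, V6 is the only scheduled biochemistry inside the window. The remaining 28 − 9 = 19 to 28 − 5 = 23 days then contain no scheduled blood or urine test that can count.

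**Which events are affected.** The following are removed in turn:

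1. Events with earlier symptoms. They are dated from the symptoms, so the sampling-date rule does not move them out of the window. Neutropenia with fever and thrombocytopenia with bleeding normally belong here.
2. Serious events. Section 11.3 defines grade 4 as life-threatening, and 12.1 makes life-threatening events serious. If the word severe in 1.6(2) means serious, one related grade 4 event stops escalation on any day.
3. Laboratory abnormalities lasting 7 days or less under medical intervention, which 1.6(1) exempts.

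What remains is mainly related, non-serious, symptom-free grade 3 non-haematological laboratory toxicity that does not resolve within 7 days under treatment. Sampled first at V7 on day 28, it counts towards expansion; on day 29, it does not.

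**Dose step if nothing intervenes.** 1/0.6 = 1.67; 2/1 = 2; 3.3/2 = 1.65.

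**The proposed window.** The later of day 28 and V7, for V7 on days 25 to 31, is 28, 28, 28, 28, 29, 30, 31. No permitted V7 day lies outside it, and no day that counts now is lost. A window ending at V7 alone would lose 3, 2 or 1 days when V7 is on day 25, 26 or 27.

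**The case against.** **The two time points are nominally the same.** In 1.3, 4 weeks and 28 days stand in one paragraph, and V7 can be seen as the day-28 assessment with an ordinary tolerance. That is probably the intention. But the protocol does not say that a V7 result counts as a day-28 result, and the sampling-date rule in 11.2 points the other way.

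**The trigger itself is unclear.** 1.6(1) needs two patients. Read strictly, one patient's listed toxicity would trigger no expansion on any day, and the window would not be the cause. This stands as a separate ambiguity. The point here rests on the reading that gives the one-patient rule something to do for these toxicities.

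**1.6(2) may already cover grade 3.** Section 11.3 labels grade 3 as severe and includes hospitalization in its description. If severe in 1.6(2) meant grade 3, one related event would stop escalation at any time. That reading would leave the two-patient rule for grade 3 in 1.6(1) with almost nothing to do, and the flowchart appears to use severe adverse events for serious ones. It cannot be ruled out, and it would narrow the point further.

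**Nothing is hidden.** This stands in full. The 4-week evaluation is mandatory, the result is available there, 1.6(1) still applies if a second patient is affected, and 1.6(3) allows a stop. But 1.6(3) is a matter of judgement and concerns stopping, not expansion.

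**A stronger reading to avoid.** A reader might infer that the 7-day exemption opens a second gap, because a result first sampled at V7 cannot have lasted more than 7 days until V7 + 8, days 33 to 39. The text does not support this. Section 1.3 asks whether the event occurs in the window, not whether its duration is settled by then, and an abnormality still open at V7 has not met the exemption. Nor does the long interval to V8 mean it goes unchecked: under 1.4, "the situation should be documented in detail and followed up until the outcome is clear".

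**Conclusion.** The mismatch is in the text, and its consequence is narrow. On 3 of 7 permitted V7 days, a qualifying laboratory toxicity first found at the gate visit triggers no automatic expansion. This rests on three assumptions: one patient with a 1.6(1)-listed toxicity triggers expansion, severe in 1.6(2) means serious, and the 28 days are counted exactly.

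A reader might take 3 of 7 as the share of toxicities missed. It is only a count of permitted days. If V7 were equally likely on each day (an assumption), the chance that at least one of three patients has a late V7 would be 1 − (4/7)³ = 81.3%. That is the chance of a late visit, not of a lost event. The frequency of lost events would need the toxicity risk and the share first seen at V7, and the protocol gives neither. Nor do the documents support saying that escalation would proceed in ignorance of the result. Only the automatic rule is lost. Severity: minor.

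**What to change.** In 1.3, write along these lines:

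> The evaluation window runs from dosing through day 28 or completion of visit V7, whichever is later. It applies to the first three patients and, as a minimum, to any three added patients. A qualifying laboratory abnormality still open at V7 counts unless it is shown to resolve within 7 days under medical intervention.

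The provisions of 1.6(2) and 1.6(3) stay as they are. Alternatively, set the V7 tolerance to −3/+0 days. That closes the gap for visits held on time, but a late visit would reopen it.

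The cost is a few sentences. The gate already waits for the 4-week evaluation, so the longer window adds no delay by itself. Showing that an open abnormality resolves may take a wait of about 8 days after V7 and one repeat test. An occasional extra expansion adds three patients and roughly 4 + 4 = 8 to 8 + 4 = 12 weeks (cell culture plus evaluation, before recruitment and screening). Full expansion of the first three groups still gives 24, the planned maximum.

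### All six patients at the highest planned dose (group 4, 3.3 times standard) may be treated before any required 28-day review of the first three

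*Protocol*

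**What the plan says.** Protocol section 1.3 gives a general size, "Each dose group will enroll around 3-6 patients", and repeats 3-6 for groups 1, 2 and 3. Group 4 is different: "The fourth group with 6 patients, receiving a single administration at 3.3 times standard dose". Group 2, at 1 times standard, is described as "the median safe dose in the previous clinical trial". Section 1.6(4) names 3.3 times as the highest dose.

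The review rule is: "Before starting the next dose group, safety evaluation must be done for 3 patients of the current dose group at 4 weeks post-transplantation". If one patient in a group has a terminating event within 28 days, three more are enrolled in that group, and "the next dose group cannot start unless none of the new enrolled 3 patients undergo adverse events that would terminate the study".

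Section 1.6 opens its first criterion with "Dose escalation should be terminated with one or more adverse events". These must be same or similar related toxicities in at least two patients of one group. Two further criteria have no two-patient threshold: "Acute IPF exacerbation and severe adverse events that are related (possibly, probably or definitely related) to REGEND001 cell therapy" and "Adverse events that making investigator and sponsor believe the dose should not be escalated anymore, regardless of the event grade or reason". Section 9 makes meeting these criteria a ground on which the trial may be halted, and lets the sponsor suspend at any time. Section 12.2 requires the investigator to report serious adverse events to the sponsor at once. Section 1.7 plans 15-24 patients in total.

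**The concern.** Safety and tolerability are the primary purpose (section 1). The protocol treats 28 days of observation in three patients as what must be known before patients in the next group are exposed. At the top planned dose it does not ask for that before three more patients are exposed to the same dose. There is no later planned group whose opening would force the review.

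The safeguards in sections 1.6, 9 and 12.2 act once an event is known, or at someone's discretion. In the section 1.4 flowchart the first post-dose blood count and biochemistry are at V6, one week after treatment, while several section 1.6(1) criteria are defined by laboratory values. Nothing prevents patients 4-6 from being dosed before those results exist for the first three. At stake is whether three patients receive the highest dose when the first three have already shown that it should be held.

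**Working it through.** **1. Is six deliberate?** Summing the group sizes reproduces section 1.7:
- Minimum: 3 + 3 + 3 + 6 = 15.
- Maximum: 6 + 6 + 6 + 6 = 24.
- If group 4 were also 3-6, the minimum would be 3 + 3 + 3 + 3 = 12, which is not the stated figure.

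So six is the intended size of group 4.

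**2. Does the three-more rule supply the pause?** It is worded for any dose group, so its first half reaches group 4. On top of six, it would give 6 + 3 = 9 patients and a maximum of 6 + 6 + 6 + 9 = 27, above 24. It fits only if the second three are themselves the expansion, and section 1.3 does not say so.

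**3. How large is the dose step?** Relative steps are 1/0.6 = 1.67, 2/1 = 2.0 and 3.3/2 = 1.65.

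**4. What could a pause spare?** The protocol gives no event rate. Assume each patient has probability p of a terminating event (as section 1.3 counts it) within 28 days, independently, for p from 0.1 to 0.5. Let X be the number of events in the first three, X ~ Binomial(3, p).
- P(X = 0) = (1 − p)³; P(X = 1) = 3p(1 − p)²; P(X ≥ 2) = 1 − P(X = 0) − P(X = 1).
- If every one-event review continues: expected patients dosed = 6 − 3·P(X ≥ 2); expected events avoided = 3p·P(X ≥ 2).
- If every one-event review stops: expected events avoided = 3p·P(X ≥ 1).

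| p | P(X = 1) | P(X ≥ 2) | Dosed, reviews continue | Events avoided, reviews continue | Events avoided, reviews stop |
|---|---|---|---|---|---|
| 0.1 | 0.243 | 0.028 | 5.92 | 0.01 | 0.08 |
| 0.2 | 0.384 | 0.104 | 5.69 | 0.06 | 0.29 |
| 0.3 | 0.441 | 0.216 | 5.35 | 0.19 | 0.59 |
| 0.4 | 0.432 | 0.352 | 4.94 | 0.42 | 0.94 |
| 0.5 | 0.375 | 0.500 | 4.50 | 0.75 | 1.31 |

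Example at p = 0.3: P(X ≥ 2) = 1 − 0.343 − 0.441 = 0.216; events avoided = 3 × 0.3 × 0.216 = 0.19.

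The comparator is six patients dosed whatever happens. Any reactive stop under the present text would already spare some patients, so for a given review policy each figure is an upper bound.

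**The case against.** The strongest reply is that nothing is misstated. Each dose level is reviewed at 28 days before the next opens, no group is staggered within itself, and staggering is a further safeguard that a reviewer happens to prefer. Group 4 opens only after the 2-times group has been reviewed, and 1.65 is the smallest relative step in the trial. A single related exacerbation or severe event already meets section 1.6(2), and so section 9(1). Autologous cultures of 4-8 weeks make some natural spacing likely. At rates of 0.1 to 0.2 the gain, with reviews continuing, is only 0.01 to 0.06 events.

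Most of this stands, and it limits the point. It does not remove it: natural spacing is not required, section 9 is permissive, and the reactive criteria need an event to have been recognised.

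Three stronger readings are tempting and not supported:
- A reader might infer that group 4 has no stopping protection. Sections 1.6, 9 and 12.2 show otherwise.
- A reader might infer that the protocol plans nine patients in group 4. The total of 15-24 points to six as its ceiling.
- A reader might infer a leap to an untested dose from the factor of 3.3 over the previous trial's median safe dose. The ladder passes through 2 times, and the doses above that median in the earlier trial are not given.

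**Conclusion.** The gap is real and rests on the text alone: group 4 is six outright, and no provision makes patients 4-6 wait for a 28-day look at the first three. The same absence applies to groups 1-3. Group 4 merits the change because it is the top planned dose and its second three do not depend on any result.

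The size depends on assumed rates of 0.1 to 0.5. The chance that a look would find two or more events is 3%, 10%, 22%, 35% and 50%. Expected events avoided are 0.01, 0.06, 0.19, 0.42 and 0.75 if every one-event review continues, all against a comparator without reactive stops. The gain is small if the dose is safe and material only if it is not. Confidence is high in the reading of the text and lower in the practical size. This is a cheap improvement.

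**What to change.** In section 1.3, dose group 4 as 3 + 3. Complete the 28-day evaluation of the first three before the second three are dosed, and state that the second three are the expansion, so the group ends at six and the total stays within 15-24.
- No terminating event in the first three: continue.
- Exactly one, including a single event under section 1.6(2): dose the second three only after a documented review by investigator and sponsor.
- Two or more: hold dosing of the second three.

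State openly that the documented review and the hold are new within-group rules for group 4. The review adds to the three-more rule, which requires none. The hold does not need the events to be alike, as section 1.6(1) does. Section 1.6 itself is unchanged.

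**Cost.** A few sentences, plus delay:
- If the second three's cells are made ahead and cryopreserved (provided for in section 5.2), about 4 weeks: 4/78 = 5% of the planned 18 months. Recovery, culturing and testing after thawing come on top.
- If the second three are brushed when the third patient is dosed, the 4-8 week culture covers the 28 days and mostly avoids freezing. The delay is then about 4-8 weeks, 4/78 to 8/78, or 5-10%.

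The slack may be thin. Assume groups run one after another with 2 weeks' screening and 24 weeks' final follow-up. With an 8-week culture the plan already uses 3 × (2 + 8 + 4) + (2 + 8 + 24) = 76 of 78 weeks; with a 4-week culture it uses 3 × (2 + 4 + 4) + (2 + 4 + 24) = 60. Overlap or expansion would shift this.

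There is also a small risk that a progressing patient fails the baseline recheck (at most two are allowed, section 5.2), or that a patient is brushed and then not treated.
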